Title: Electro-acupuncture (EA) in Children Undergoing Procedures for Congenital Heart Defects.

NCT number (unavailable),

Date 9/20/2017

Primary investigator: [name] MD

Affiliation: West Virginia University, Morgantown, WV

Address: [name]
[name]
[name]

Research plan

Background

Managing the child with congenital heart disease has become increasingly complex. The goal is to not only have the child survive, but has him or her recover with *comfort* and preservation of the heart and other vital organs through *reduced complications*. Despite optimal pharmacologic management, these problems continue to occur. Additionally, recent concerns about the crisis surrounding opiate use/abuse have had an effect reducing the use of these drugs even in situations where they are indicated.

Moving beyond pharmacologic strategies is one way to consider reaching the goal of increased comfort and reduced complications. Acupuncture has been used for centuries to diagnose and treat a variety of medical conditions and is the practice of using certain anatomical points to achieve well-being in the patient. Conventional acupuncture techniques involve needle manipulation at a specific anatomical point, but this approach may be difficult, if not impossible, to use in the operating room (OR) because of physical access and time constraints.

Electro-acupuncture (EA) can achieve the results of standard acupuncture with less time and utilizes electric current instead of needle manipulation to achieve its effects. The electric stimulation is provided through an acupuncture needle or a small electrode pad, and can be transmitted using different wave forms. These waveforms have the following theorized advantages¹: Continuous and/or a dense-disperse wave for analgesia, and dense-disperse wave for blood circulation.

With electro-acupuncture, the stimulation frequency plays an important role in the release of naturally occurring analgesics. Evidence suggests that lower frequencies (2 Hz) result in the release of enkephalins and endorphins, whereas higher frequencies (100 Hz) result in the release of dynorphins.² Varying between high and low frequencies (continuous plus dense-disperse) endogenous opioid peptides should release resulting in their synergistic interaction.

There is controversy about the optimal current. Most studies have used current in the milliamperage range and adjusted the current to be just below the threshold where electrically stimulated movement is observed, or typically in the mid-range (1-14mA). In contrast, there is a belief that the optimal current utilized should be in the microampere range. The Arndt-Shultz Law postulates that weak currents increase physiologic activity while strong current inhibit it. Adherents believe that micro currents (50 microamps -1000 microamp (1 Milliamp)) increase ATP concentrations while currents above 1000 micro amp do not increase ATP production and higher currents 5000 microamps may decrease ATP. Micro current techniques have been shown to increase microvascular blood flow, enhance circulation, reduce edema, and stimulate the growth of new blood vessels which significantly increases angiogenesis and tissue perfusion.³

Current literature discussed below identifies a number of points that experienced acupuncturist have found effective in dealing with issues encountered during cardiac surgery. The only recent pediatric cardiac acupuncture study was a randomized control trial done by Ni X et al.⁴ Their study looked at 70 non-complex congenital heart patients age 2-12 that underwent cardiopulmonary bypass (CPB) with an aortic cross clamp. They stimulated point pericardial 6 (PC 6) bilaterally for 30 min using a dense-disperse wave at a frequency of 2 Hz. The mean amplitude used was 14±3mA. Lower troponin and C-reactive proteins were observed in children receiving stimulation. Shorter ventilation times, shorter PICU stays, higher levels of naturally occurring pain killers (β -endorphin) and lower levels of stress hormones (serotonin levels (5-HT)) were seen in the EA group.

Other adult cardiovascular studies have found similar advantages of stimulation of the PC-6 point. Ma et al. found that EA stimulation at PC 6 for 30 minutes before and during cardiac valve replacement had a positive effect on ischemic re-perfused myocardium by alleviating oxidative stress injury.⁵ The patients receiving EA at PC 6 had higher superoxide dismutase levels and lower troponin levels than the control group.⁴ Yang et al. stimulated PC 6 along with LieQue lung (LU) 7 and Yunmen LU 2 at 0.8-1.9 mA and frequency of 5 and 30 Hz for 30 minutes for 5 days before valve surgery. The EA group had shorter ICU stays and significantly lower troponin I levels at 6, 12 and 24 hours after cross clamp removal. Inotropic scores were also significantly lower at 12, 24 and 48 hours after ICU arrival.⁶

To optimize the effects of EA, there is a question as to when the EA should be initiated and how long it should be continued into the postoperative period. Adult studies have employed preoperative treatments from one hour to 3 days in advance of the procedure, then intraoperative therapy followed by post-operative therapy. Chen et al. performed EA at 30 minutes prior and continued their therapy postoperatively every 12 hours for 3 days. Their treatment group had lower serotonin levels, less nausea, required less analgesics, and had higher β -endorphin levels at 24, 48 and 72 hours post-operative than the sham EA group.⁷

Not only is the comfort of the patient increased, but acupuncture techniques have been shown to decrease complications. Qiang et al. added PC 4 to PC 6. They stimulated for 30 minutes one to two hours prior to the procedure. Compared to their control group that did not get EA, the EA treatment group (stimulated with 2 and 15 Hz at 7-11mA) had a decreased incidence of major adverse cardiac and cerebrovascular events (odds ratio 0.327, 95% CI 0.140–0.767, *P*

= 0.010) at 24 months. They also found significant reduction in myocardial infarctions based on in serum troponin levels at 24 hours after percutaneous coronary intervention.⁸

The effects of EA do dissipate, but these techniques do not necessarily need to be started before the incision or insult. Syuu et al. looked at the effects of EA at PC 6 in a hemorrhaging dog model. EA was started 30 after the hemorrhage was initiated. This study illustrated that stimulation of PC 6 prevented the fall in left ventricular performance and rise of plasma vasopressin. Improved left ventricular performance was also noted as long as EA was maintained. Once the stimulation was stopped, the effects dissipated over 120 minutes. This confirmed that stimulation of the point can be initiated after incision or insult, and that the effects of EA dissipate over time.⁹

Though stimulation at PC-6 has been done by many investigators, other points have been used as well for cardiovascular surgery. Zhou et al. studied 100 patients with standard general anesthesia and 100 patients with combined acupuncture plus midazolam.¹⁰ Those in the acupuncture group had significantly less opiate use, fewer pulmonary infections, shorter ICU stays, and lower cost. The points stimulated for this study were ZhongFU (Lung 1), Lung 7 and PC 4.¹⁰ Points used by Chi et al. included Lung 1, Chize (Lung 5) and PC 4.¹⁰ Their acupuncture group needed significantly less blood transfusion, less antibiotics for pulmonary infections, and had shorter duration of hospitalization, shorter ICU stays and lower medical costs. They stimulated their points at 3-4 Hz and 2.0-2.2 mA for 20 minutes.¹¹ A common point in these papers was stimulation at PC 4 and PC 6. Another advantage of these points is that they are distal to the surgical field and usually readily accessible.

Stimulation at PC 6 has advantages in the kidney as well. Fifty percent of children undergoing cardiovascular surgery develop at least stage 1 acute kidney injury (AKI). It is speculated that this AKI is related to activation of sympathoexcitatory inputs modulated through renal afferent nerves. Recent studies have tried to decrease this incidence by modulation of the renotubular feedback loop with adenosine receptor antagonism¹¹ This has been able to decrease the need for renal replacement therapy after CPB, but has not been shown to prevent the development of AKI.¹² EA can affect sympathoexcitatory inputs. Yu et al. stimulated rabbits in an AKI model and found stimulation at PC 6 and ST 36 using a dense disperse wave at 2 and 15 Hz with 1 mA reduced morphologic renal damage and attenuated renal tubular apoptosis.¹³

A special consideration during cardiac surgery is that organ blood flow is also often affected by non-pulsatile flow or hypotension. Lele et al., in a controlled hypotension model in dogs, found that EA helped maintain better blood flow to the stomach and kidney, resulting in reduced apoptosis in those organs. Further, the apoptosis that was observed in the control animals' brains did not occur in the animals receiving EA. Points used were large intestine (LI)-4, ST-36 spleen (SP)- 6 and LI-11 stimulated bilaterally at 2 Hz with 3-5 mA.¹⁴

Research Plan:

This study will help to identify whether electroacustimulation is a beneficial anesthesia adjunct in children undergoing procedures on their congenital heart defects.

Electroacustimulation is a technique with minimal risks, which enhances the body's innate abilities to deal with the stresses and pain of surgery. Our goal is to optimize care for those patients with congenital heart disease by increasing *comfort* and *reducing complications*. This study will examine comfort using age appropriate pain scoring systems. The complications this study will focus on are myocardial injury which will be assessed by measuring Troponin levels, and renal injury assessed using AKIN criteria

Treatment Groups:

Subjects will be randomized. Randomization will be done using block randomization with block sizes between 4 and 8. The sham procedure will use the identical set up as the treatment group, but those participants in the sham group will not receive the electro-stimulation.

Group 1: Will have electrodes placed at Pericardial 4 and 6, Large Intestine 4, and Stomach 36 and receive electroacustimulation (treatment) frequency will be at 2Hz and 100 Hz the amplitude will be 1000mA.

Group 2: Will have electrodes placed at Pericardial 4 and 6, Large Intestine 4, and Stomach 36 and receive sham electroacustimulation (control) will not have stimulation.

Duration of Treatment:

The duration of treatment (stimulation or sham) for subjects will be length of surgical procedures on their congenital heart defects. Patients will be followed for 6 hours to collect data on myocardial injury and 48 hours to collect data on pain, and renal injury.

Objectives:

Primary Objective:

The primary objective of this study is to identify whether electroacustimulation is a beneficial anesthesia adjunct in children undergoing procedures on their congenital heart defects. Does it decrease myocardial injury and or need for myocardial support. Differences between the groups Troponin I levels pre-operative and six hours postoperative will be evaluated.

Secondary Objectives:

1) Evaluate the incidence discomfort in the post- operative period.

To evaluate the incidence and severity of pain assessed by using age appropriate West Virginia University Hospital approved nurse guided pain scoring the Neonatal/Infant Pain Scale (NIPS) (children age birth to 2 months) FLACC (2 months to 7 years or unable to communicate, or VAS(age 8-18) every 2 hours for 48 hours post procedure.

2) Determine the incidence of Acute kidney injury (AKI) between these two treatment groups. Acute Kidney Injury will be evaluated by AKIN criteria. Creatinine and urines will be measured at 6, 12, 24 and 48 hours after bypass.

Need for post-operative myocardial support:

To assess the need for myocardial support an inotropic score will be used and compared between the two groups. The Inotropic score will be evaluated every 6 hours for 48 hour between the 2 groups

Study Design:

This is a single site, randomized, blinded, sham controlled, parallel group study to identify whether electroacustimulation is a beneficial anesthesia adjunct in children undergoing procedures on their congenital heart defects.

Study subjects age's birth to eighteen years, undergoing cardiac surgery for their congenital heart lesions will be considered for entrance into the study. The randomized subjects will receive either electrostimulation or sham during their surgery for CHD. Subjects are expected to remain in the hospital 48 hours post procedure. Standard of care blood samples will be obtained pre-operative and post-operative. The only study specific blood sample will be Troponin I levels which will be obtained presurgically after the lines have been placed and a 6 hours post bypass/aortic clamp removal. Urine samples will be obtained pre-surgically after placement of the Foley and every 6 hours post bypass for 48 hours while the Foley catheter is still in place .

Number of Subjects planned:

Approximately 108 patients, over the two years, with randomization of 54 allocated to each group.

- Electroacustimulation (treatment) frequency will be at 2Hz and 100 Hz the amplitude will be 1000mA.
- Sham electroacustimulation (control) will not have stimulation

Study Population:

Inclusion criteria:

Subjects must fulfill all of the following inclusion criteria to be eligible for participation in the study:

- 1) Patients 0-18 years of age undergoing procedures on their congenital heart defects.
Additionally, patients with coarctation of the aorta for repair will be considered as a separate group and eligible for enrollment.
- 2) Willing to provide written Assent/Consent in English.

Exclusion criteria:

Subjects will be excluded if they fulfill any of the following exclusion criteria:

- 1) Patients with skin lesion over more than 50% of acupuncture sites.
- 2) Patients in renal failure.
- 3) Patients on chronic opioid therapy.
- 4) Unwilling to provide written Assent/Consent in English.

Concomitant Treatment:

All subjects will receive a standard anesthetic of propofol, remifentanyl and dexmedetomidine at doses needed to maintain a stable BIS number and lack of movement. When possible neuromuscular blocking agents will not be used. A morphine infusion will be used for postoperative pain control based on need. Those allergic to morphine will receive a substitute opiate by continuous infusion.

Study Procedures:

Screening:

Review of consent form- Subjects that provide written assent/consent and meet all inclusion and no exclusion criteria will be included into the study. Subjects may withdraw consent to participate at any time. Participation in the study is voluntary. Adverse events will be recorded after informed assent/consent obtained.

Surgery: Treatment/Sham

Eligible subjects will undergo blood sampling (3.5cc) and urine sample (0.5-2cc) will be obtained prior to stimulation/sham.

All subjects will have electroacustimulation pads applied at four points bilaterally: pericardial 4 (PC 4), pericardial 6 (PC 6), large intestine 4 (LI 4) and stomach 36 (ST 36). No needles will be used. ([Appendix A; 1](#))

Subjects will be randomized. Randomization will be done using block randomization with block sizes between 4 and 8. The sham procedure will use the identical set up as the treatment group, but those participants in the sham group will not receive the electro-stimulation. Stimulation/sham will begin as soon as possible after induction of anesthesia and obtaining baseline laboratory samples of urine and blood.

Group 1: Receive electroacustimulation (treatment) frequency will be at 2Hz and 100 Hz the amplitude will be 1000mA.

Group 2: Receive sham electroacustimulation (control) will not have stimulation. Subjects will undergo procedures on their congenital heart defects.

Blind:

The anesthesia provider will be blinded as to whether the electroacustimulation device is actually turned on or not. The research coordinator will hold the blind. The electroacustimulation machine will be placed in an opaque bag to secure the blind. The current is below the threshold to stimulate the muscle so that no movement will be visible. It is also below the sensory threshold so that it will not produce any discomfort in the subjects.

Stimulation/Sham will be continued until the patient is ready for transport to the PICU.

Post-Operative: PICU

Stimulation/Sham will be discontinued.

PICU care givers will be blinded as to which group the patients were randomized.

Subject comfort will be assessed using age appropriate West Virginia University Hospital approved nurse guide pain scoring based on Universal Pain Assessment Tool or the Neonatal/Infant Pain Scale (NIPS) will be recorded in the electronic medical record (EMR) every 6 hours for 48 hours.

The amount of opiate infused, Nausea, Vomiting, and urine output will be assessed every 6 hours for the first 48 hours and recorded in the EMR.

Research blood samples for troponin I will be obtained at 6 hours post surgery. Total amount of 7cc of blood will be

obtained for this study. WVUH lab will process samples.

Research urine samples (.05-2cc) will be collected at 6, 12, 24, and 48 hours after bypass. The urine samples will be stored in a -80 degree freezer and analyzed by ELISA testing at the end of the study for Superoxide dismutase, Neutrophil gelatinase – associated lipocalin (NGAL), WNT4.

AKIN criteria will be used to evaluate AKI every 6 hours. Inotropic score will be recorded every 6 hours.

Daily chest x-ray will be used to assess pulmonary status.

The AKIN criteria, inotropic scores, chest x-ray and creatinine levels, (used for AKIN), are standard of care measurements and the data will be collected for this research project.

An Electrostimulation Documentation Guide has been developed for the staffing. (Appendix A2)

Tool/Instruments to be used in data collection:

Tools and instruments for data collection: secured Excel data base; Neonatal/Infant Pain Scale (NIPS); AKIN stage; Inotropic Scores; RACHS categories (Appendix A3-6).

Variables:

Detailed descriptions of the variables are given in Appendix B. The information collected for each patient will include the following variables. *Outcomes:* Pain score; inotropic score; Narcotic use; renal laboratory values: creatinine, neutrophil gelatinase-associated lipocalin (NGAL), WNT4, AKIN score; superoxide dismutase; indicator for pneumonia; time-to-extubation (intubation time, extubation time); length of pediatric intensive care unit (PICU) stay (arrival time, discharge time). *Other variables:* Age, sex, cardiac defect, cyanosis, RACHS score, cardiopulmonary bypass time (CPB), cross clamp time and surgery start and end time, occurrence of nausea, vomiting event, urine output, number of lobes with atelectasis.

Analytic methodology

Randomization: Eligible participants will be randomized to the acupuncture treatment or control group using a randomly varying block randomization method to ensure equal distribution among treatment groups.²² The project statistician, who will have no contact with the participants or any of the personnel assessing the patients, will generate a randomized assignment master list and provide this information only the study personnel who will be setting up the acupuncture device. Each participant will be assigned a unique number that will follow the patient through the study. The study number and participant's name will be retained on a secure electronic database; this information will be linked to the randomization assignment to create a crosswalk file. It will be stored in a separate password-protected database. At the end of the study, the cross-walk file will be used to link the patient data and treatment allocation.

Sample size:

Predicated on the primary aim, the sample size for this pilot study we used a two-sided two-sample t-test with unequal variance t-test with an alpha level of 0.05 and power of 80%. A morphine equivalent dose of 0.71 mg/kg was used for the control group and 0.57 mg/kg for the acupuncture group. This represents a conservative 20% change between the control and acupuncture group. The standard deviation of the control group was estimated to be 0.3 mg/kg for the control group and 0.2 for the experimental group. **The total estimated sample size is 108 patients, over the two years, with 54 allocated to each group.** Historically, we would have had a potential enrollment and retention of approximately 74 patients per year accounting for a 25% non-consent rate and a 2% drop-out rate. This project is well powered for statistical significance and feasibility for a 2-year study.

Data collection:

The data will be retrieved from the EMR and imported or entered into a secured EXCEL database.

Statistical analysis plan:

For all aims, univariate statistics (e.g. mean, median, standard deviation, min, max and skew) will be used to describe the collected data. Parametric approaches (e.g. t-test, Pearson's correlation, and chi-squared test) will be used when the data satisfy the required statistical assumptions; they will be used to compare the demographic and clinical characteristics between treatment and control. If the distributional assumptions are untenable, then the Mann-Whitney test, Spearman

correlation, and Fisher's exact test will be used. We will use the Box-Cox or the exponential transformation when the absolute value of skew is greater than 0.4.

To address the overall difference between the control and the acupuncture group, we will look at the score changes between baseline and 48 hours. For the continuous outcomes, a t-test based on the difference in outcome will be used to compare the two treatment groups. For the categorical outcomes, a logistic regression model (generalized linear model with binary or multinomial outcome) will be used to compare the two treatment groups' at baseline and 48 hours. The generalized linear hypothesis methodology will be used to contrast the two time points. This approach will provide consistency of modeling methodology for the secondary analyses. Adjusted models will be considered (e.g. glm regression with identity and/or logit links) to account for any data imbalances, potential confounders, etc. Minimally, a RACHS score adjustment will be assessed for its relevance.

A secondary analysis will be used to describe the longitudinal (repeated measures) outcome trends. A generalized linear mixed-effects regression model will be used for longitudinal data. Both unadjusted and adjusted trends will be assessed. We will account for both heteroscedasticity and autocorrelation variance-covariance structures. The generalized linear model approach will permit trend characterizations for either continuous or categorical outcomes under the same generalized linear model framework.

[figure not shown]
All results, predicated on formal hypothesis testing methodology, will use an alpha-level of 0.05 for statistical significance. Bonferroni or Scheffe adjustments will be used, when appropriate, to retain the family-wise alpha level of 0.05 when performing multiple tests under the same global hypothesis or construct. Every effort will be used to ensure all relevant information is collected. In the event of missing data, generalized estimating equations for longitudinal analysis will be used. All statistical analysis will be done using the most recent version of the R language for statistical computing and graphics.

Tentative time table: Approximately 2 years to enroll 108 subjects.

[figure not shown]
References:

- 1) Instruction manual for KWD-808I Multipurpose health device, Ying Di page 21.
http://www.ib3health.com/products/Acupunctoscope/KWD808_I.asp#808I_Instruct [Accessed Sept. 5, 2016]

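### Eligibility does not screen for implanted electronic devices, so a child with a pacemaker or defibrillator could be randomised to electrical stimulation

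*Combined protocol and SAP*

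**What the plan says.** **Who may enter.** The first inclusion criterion under Study Population is "Patients 0-18 years of age undergoing procedures on their congenital heart defects". Coarctation repairs are also eligible, as a separate group. The exclusions are "Patients with skin lesion over more than 50% of acupuncture sites", "Patients in renal failure", "Patients on chronic opioid therapy", and unwillingness to consent or assent in English. Under Screening, a consenting child who satisfies these lists is included, and no further check is described.

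**What is given.** Under Surgery: Treatment/Sham, "All subjects will have electroacustimulation pads applied at four points bilaterally": two pericardial points, one large intestine point and one stomach point. The treatment arm receives 2 Hz and 100 Hz, with the amplitude printed as 1000mA. Stimulation starts soon after induction and runs until the child is ready to leave for intensive care. No number of hours is stated.

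**Who knows.** Under Blind, the anaesthesia provider is not told whether the device is on, and "The electroacustimulation machine will be placed in an opaque bag to secure the blind". The research coordinator keeps the allocation. Under Randomization, the staff who set up the device also receive it.

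**What is said about safety.** The Research Plan states that "Electroacustimulation is a technique with minimal risks". The Blind section adds that the current is too low to move muscle or to be felt.

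**The concern.** The intervention is electrical and the patients have heart disease, yet the only exclusion tied to the stimulation itself concerns the skin under the pads. A pacemaker or defibrillator acts on electrical signals that it senses. Whether this stimulation could affect one is a question the plan should answer before such a child is randomised. That possibility is general reasoning, because the documents discuss no interaction with implants.

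Any hazard would fall only on the stimulated arm, would be added by the trial itself, and would be concealed from the anaesthesia provider. Because device status is not collected, the data would not show afterwards that such a child had been enrolled.

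**Working it through.** **1. Is there a screen anywhere?**

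| Place | What it covers | Implanted device? |
|---|---|---|
| Inclusion criteria | Age, congenital heart procedure, consent | No |
| Exclusion criteria | Skin, renal failure, opioids, English consent | No |
| Documentation guide, baseline table | Creatinine, urine, RACHS score, cyanosis | No |
| Appendix B, other variables | Demographics, defect, cyanosis, RACHS score, procedure times, nausea, vomiting, urine output, atelectasis | No |

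Pacemakers, defibrillators and other active implants are mentioned nowhere in the protocol or analysis plan. Followed literally, the entry rule admits a child who has one.

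**2. Does the stated current settle the matter?** The Blind section's assurance concerns the child's muscle and sensation. It does not say what an implant would detect. The amplitude is also inconsistent:

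- Treatment Groups, Number of Subjects planned and Surgery: Treatment/Sham all print 1000mA, which is 1000 × 1000 = 1,000,000 microamps.
- The Background describes microcurrent as 50 to 1000 microamps. The printed figure is 1,000,000 / 1000 = 1000 times the top of that range.
- The Background gives 1 to 14 mA as the typical milliampere range. The printed figure is 1000 / 14 ≈ 71 times the top of that range.

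The documents must be reconciled. Until they are, the threshold statement cannot be used as a safeguard.

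**3. Can recruitment bear another exclusion?** The plan's target comes first. Inputs from Sample size are a difference of 0.71 − 0.57 = 0.14 mg/kg, SDs of 0.3 and 0.2, two-sided alpha 0.05 and power 80%.

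- Normal approximation: n = (1.960 + 0.842)² × (0.3² + 0.2²) / 0.14² = 7.85 × 0.13 / 0.0196 ≈ 52.1, so 53 per arm.
- Unequal-variance t-test: the smallest n is 54 per arm, with power 80.6%. The total is 108, as stated.

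The projection is "approximately 74 patients per year", already net of 25% non-consent and 2% drop-out:

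- 74 × 2 = 148 over two years
- 148 − 108 = 40 spare
- 40 / 148 = 27%, the share that could be lost before the projection falls below target

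**4. How many children?** The documents give no prevalence. Purely as an assumption, take 1% to 5%:

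- Among 108 randomised: 1.1 to 5.4 children, so 0.5 to 2.7 in the stimulated arm of 54.
- Lost from the projected 148: 1.5 to 7.4, leaving about 141 to 147.

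**The case against.** The strongest reply is that the hazard is not in the documents. They report no interference, no device prevalence and no heart-rate data, and they describe a current too weak to move muscle or be felt. Precautions may also appear in the consent form or in the manufacturer's manual (reference 1), neither of which was available. This stands as a limit on size: nothing here shows that an interaction would occur or how often. It does not fill the gap, because the eligibility list decides who is randomised and it is silent.

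A second reply is that the blind is not total. Pads and machine are attached in both arms, the coordinator and set-up staff know the allocation, and adverse events are recorded from consent. That is correct. However, no text makes any of these people responsible for checking for an implant, and no emergency unblinding procedure is described.

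A reader might infer more than the text supports:

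- **Hours of exposure.** Duration is tied to the procedure and never quantified.
- **Re-operated children arriving with devices.** The RACHS appendix is a list of procedures by risk category. Two entries involve removing a pulmonary artery band, which implies earlier surgery, but none mentions an implant.
- **A pulse rate resembling a heartbeat.** 2 Hz is 2 × 60 = 120 pulses per minute, but the documents offer nothing against which to judge that figure.
- **A blinded provider in charge of heart rhythm.** The plan says only that the anaesthesia provider is blinded. It does not assign rhythm management.

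**Conclusion.** The omission is real and nothing in the protocol or analysis plan makes up for it. As written, a child with a pacemaker or defibrillator would be eligible, could be stimulated, and would not be identifiable in the data.

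This is a patient-safety point and a cheap improvement. It is not a threat to the trial's conclusions. A reader might infer that altered pacing would bias troponin or inotropic score. That would require a device to be present, to sense the current, to change its pacing, and then to shift the outcome. Even under the assumed 1% to 5%, this concerns at most about three of 54 stimulated children, and no step in the chain is documented. The effect on the comparison would be negligible.

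The verdict rests on the silence of the eligibility criteria and data forms, and on the general premise that an implant which senses electrical signals deserves a check before current is applied. It does not depend on the assumed prevalence or on which amplitude is correct.

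**What to change.** - Add to the exclusion criteria: implanted pacemaker, defibrillator or other active electronic implant at enrolment.
- Add the same item as a yes/no field at screening, so that the check is made and recorded.
- Reconcile the printed amplitude, the microampere range in the Background and the threshold statement in the Blind section.

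**Cost.** One line of eligibility text, one screening question and a consistency correction. The sample size calculation is unchanged. The downside is a slightly narrower population: the results would not cover children with implants. The projected surplus of 40 covers the loss unless more than about 27% of otherwise enrolled children have such a device. The plan does not say whether its 74 per year already allows for the existing clinical exclusions, so the true surplus may be smaller.

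### The active arm's amplitude is written as 1000 mA everywhere it is defined, which conflicts with the protocol's own current ranges and its sub-threshold claim

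*Combined protocol and SAP*

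**What the plan says.** The amplitude of the active arm appears in three operative places, with the same figure each time:

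- Treatment Groups, Group 1: "receive electroacustimulation (treatment) frequency will be at 2Hz and 100 Hz the amplitude will be 1000mA"
- Number of Subjects planned: "Electroacustimulation (treatment) frequency will be at 2Hz and 100 Hz the amplitude will be 1000mA"
- Study Procedures, Surgery: Treatment/Sham, Group 1: "Receive electroacustimulation (treatment) frequency will be at 2Hz and 100 Hz the amplitude will be 1000mA"

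The Background sets out two schools of thought on current. Most studies worked in milliamperes, a little under the level that provokes movement, usually 1 to 14 mA. Adherents of the other school hold that "micro currents (50 microamps -1000 microamp (1 Milliamp)) increase ATP concentrations" and that "higher currents 5000 microamps may decrease ATP".

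The Blind section then describes this trial's own current: "The current is below the threshold to stimulate the muscle so that no movement will be visible". It adds: "It is also below the sensory threshold so that it will not produce any discomfort in the subjects".

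**The concern.** The stated amplitude and the sub-threshold description cannot both hold for the same stimulation, and the amplitude lies far outside every current the protocol cites. Three things are at stake.

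- **Safety.** Participants are aged 0 to 18 years and anesthetized. Pads are applied at four points on both sides, and stimulation runs from soon after induction until the child is ready for transport to the PICU. An anesthetized child cannot report discomfort. The text gives no maximum output, titration step or stopping rule for current that would catch a wrong setting.
- **Blinding.** Hiding the machine in an opaque bag does not hide muscle movement. The anesthesia provider's blind therefore relies on there being none, and Concomitant Treatment avoids neuromuscular blockers where possible, so paralysis would often not mask a twitch.
- **What was tested.** The Background presents the choice between milliampere and microampere current as unsettled, so amplitude is part of what defines the intervention. The Documentation Guide (Appendix A2) records only start and end times of stimulation or sham, and Appendix B has no amplitude variable. The planned data would not show what was delivered.

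**Working it through.** The amplitude is a device setting, not the result of a formula, so there is no derivation to reproduce. The check is a unit comparison within the protocol.

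**Inputs**

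- Stated amplitude: 1000 mA (Treatment Groups; Number of Subjects planned; Study Procedures).
- Unit equivalence given in the Background: 1000 microamps = 1 mA. Hence 1000 mA = 1,000,000 microamps.
- Reference currents: those in the table, from the Background.

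**Formula:** ratio = stated amplitude / reference current, both in mA.

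| Reference current in the Background | mA | Ratio |
|---|---|---|
| Top of the micro-current range (1000 microamps) | 1 | 1000 / 1 = 1000 |
| Level said to risk lowering ATP (5000 microamps) | 5 | 1000 / 5 = 200 |
| Top of the usual range in most studies | 14 | 1000 / 14 = 71.4 |
| Pediatric cardiac trial, mean plus one reported spread (14 + 3) | 17 | 1000 / 17 = 58.8 |

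The other currents cited are 0.8–1.9 mA (an adult valve-surgery trial), 7–11 mA (the percutaneous coronary intervention trial), 2.0–2.2 mA (another cardiac surgery study), 1 mA (the rabbit kidney model) and 3–5 mA (the dog hypotension model). All lie below 14 mA.

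**Against the Blind section**

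1. The Background says that currents tuned to sit just under the movement threshold are typically 1 to 14 mA. The movement threshold is therefore of that order.
2. The Blind section says the trial's current is under the movement threshold.
3. At 1000 mA the current would be about 71 times the top of that range, so statement 2 would be false.
4. The protocol gives no number for the sensory threshold. That this claim also fails is an inference, but a safe one at this size.

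**An alternative reading.** If 1000 microamps was meant, the setting is 1000 / 1000 = 1 mA. That is the top of the micro-current range and the bottom of the 1 to 14 mA range, and it is compatible with the Blind section. No passage states the trial's amplitude as 1000 microamps or 1 mA.

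The sample size calculation does not use the amplitude and is unaffected.

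**The case against.** The strongest reply is that this is an obvious unit slip, or even a misread symbol, and that nobody planned to deliver 1000 mA.

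- **Misread symbol.** The available text was extracted from PDF and does corrupt some symbols: the age limits in the RACHS appendix are garbled. An m in place of a micro sign is a one-character difference. This cannot be fully excluded, so the source file should be checked. It is unlikely, however: the unit reads the same all three times, the beta and plus-minus signs survive in the Background, the mu survives in the AKIN table, and the Background writes microamps out in words.
- **One slip, not three.** The wording is nearly identical in each place, so it was probably copied. That stands: the repetition is not independent confirmation. It also means that no operative section gives a correct value.
- **The intended value is evident.** The Background uses the same number in microamps, and 1 mA would fit everything else. This is the most plausible explanation, but it remains unconfirmed, and staff should not have to infer a dose.
- **The ranges are only background.** That stands too. They describe other studies and a contested belief, and they set no limit for this trial. The direct conflict is with the Blind section, which does describe this trial's current.
- **Harm is not shown.** The documents do not say what the device can deliver or what was delivered. The safety and blinding consequences concern the plan followed as written. They are not evidence of injury or unblinding.

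**Conclusion.** The concern holds, and the figure must be fixed. The amplitude that defines the active arm is wrong as written: it exceeds the usual range about 71-fold, the level said to risk lowering ATP 200-fold, and the micro-current range 1000-fold, and it cannot be reconciled with a current below motor and sensory threshold.

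This rests on the printed unit being as extracted, on the Background's own unit equivalence, and on its placing sub-movement currents at about 1 to 14 mA. It does not rest on any claim about what the device delivered, and this review does not decide which figure is right.

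**What to change.** Before any further use:

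1. Check the unit in the source file, and check the actual device setting and output limit against the manual for the device in use. The protocol cites one manual as reference 1.
2. State one verified amplitude, with its unit, in Treatment Groups, Number of Subjects planned and Study Procedures. Confirm that it is consistent with the Blind section and explain how it relates to the two current ranges in the Background.
3. Add the delivered amplitude to the Documentation Guide and to Appendix B, recorded for each patient by the unblinded staff who set up the device and kept away from blinded personnel.
4. If patients have already been treated, establish and document the setting that was used.

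The cost is a short protocol amendment, a device check and one extra record field. Sample size and analysis do not change.
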